4.2 Exclusion criteria

Patients should not enter the study if any of the following exclusion criteria are fulfilled:

1. *Involvement in the planning and/or conduct of the study (applies to AstraZeneca staff/BCA staff and/or staff at the study site).
2. *BRCAl* and/or *BRCAl2* mutations that are considered to be non detrimental (e.g., “Variants of uncertain clinical significance” or “Variant of unknown significance” or “Variant, favour polymorphism” or “benign polymorphism” etc.).
3. Cytotoxic chemotherapy or non-hormonal targeted therapy within 21 days of Cycle 1 Day 1 is not permitted. Endocrine therapy must have been discontinued 7 or more days before Cycle 1 Day 1. Palliative radiotherapy must have been completed 14 or more days before Cycle 1 Day 1. The patient can receive a stable dose of bisphosphonates or denosumab for bone metastases, before and during the study as long as these were started at least 5 days prior to study treatment.
4. *Patients with HER2-positive disease (3+ by IHC or ISH amplified ≥ 2.0).
5. *Previous randomisation in the present study.
6. Exposure to an investigational product within 30 days or 5 half lives (whichever is longer) prior to randomisation
7. *Any previous treatment with a PARP inhibitor, including olaparib.
8. *Patients with second primary cancer, EXCEPTIONS: adequately treated non-melanoma skin cancer, curatively treated in-situ cancer of the cervix, Ductal Carcinoma in Situ (DCIS), stage 1 grade 1 endometrial carcinoma, or other solid tumours including lymphomas (without bone marrow involvement) curatively treated with no evidence of disease for ≥ 5 years prior to study entry.
9. Resting ECG with QTc > 470 msec detected on 2 or more time points within a 24 hour period or family history of long QT syndrome. If ECG demonstrates QTc >470 msec, patient will be eligible only if repeat ECG demonstrates QTc ≤ 470 msec.

10. *Patients cannot have received more than 2 prior lines of cytotoxic chemotherapy for metastatic disease. Prior treatments with hormonal therapy and non-hormonal targeted therapy are allowed and not counted as a prior line of cytotoxic chemotherapy. For the purposes of this protocol, the combination of an aromatase inhibitor and everolimus is not considered cytotoxic chemotherapy.
11. *Concomitant use of known potent CYP3A inhibitors such as ketoconazole, itraconazole, ritonavir, indinavir, saquinavir, telithromycin, clarithromycin and nelfinavir. For further detail refer to Appendix I.
12. Persistent toxicities (\geq CTCAE grade 2) caused by previous cancer therapy, excluding alopecia and CTCAE grade 2 peripheral neuropathy.
13. *Patients with myelodysplastic syndrome/treatment related acute myeloid leukaemia.
14. Major surgery within 2 weeks of starting study treatment: patients must have recovered from any effects of any major surgery.
15. *Immunocompromised patients, e.g., patients who are known to be serologically positive for human immunodeficiency virus (HIV).
16. *Patients considered a poor medical risk due to a serious, uncontrolled medical disorder, non-malignant systemic disease or active, uncontrolled infection. Examples include, but are not limited to, uncontrolled ventricular arrhythmia, recent (within 3 months) myocardial infarction, uncontrolled major seizure disorder, unstable spinal cord compression, superior vena cava syndrome, extensive bilateral lung disease on High Resolution Computed Tomography scan or any psychiatric disorder that would limit ability to comply with study procedures, and any other medical condition that, in the opinion of the investigator, places the patient at unacceptable risk of toxicity.
17. *Patients with a history of treated CNS metastases are eligible, provided they meet all of the following criteria: Disease outside the CNS is present. No clinical evidence of progression since completion of CNS-directed therapy. Minimum of 2 weeks between completion of radiotherapy and Cycle 1 Day 1 and recovery from significant (Grade \geq 3) acute toxicity with no ongoing requirement for $>$ 10mg of prednisone per day or an equivalent dose of other corticosteroid.
18. *Patients unable to swallow orally administered medication and patients with gastrointestinal disorders likely to interfere with absorption of the study medication.
19. Pregnant or breast feeding women.
20. *Previous allogeneic bone marrow transplant.

21. *Patients with a known hypersensitivity to olaparib or any of the excipients of the product.
22. *Whole blood transfusions in the last 120 days prior to enrolment to the study which may interfere with *gBRCA* testing (packed red blood cells and platelet transfusions are acceptable, for timing refer to inclusion criteria no.10)

Procedures for withdrawal of incorrectly enrolled patients see Section 5.3.

5. STUDY CONDUCT

5.1 Restrictions during the study

5.1.1 Contraception

Female patients of child bearing potential and their partners, who are sexually active, must agree to the use of two highly effective forms of contraception in combination throughout the period of taking study treatment and for at least 1 month after last dose of study drug.

Male patients and their partners, who are sexually active and of childbearing potential, must agree to the use of two highly effective forms of contraception in combination, throughout the period of taking study treatment and for 3 months after last dose of study drug(s) due to the unknown effects of the study drug on the sperm. Male patients should not donate sperm throughout the period of taking study treatment and for 3 months following the last dose of study drug(s).

For details please refer to Appendix F Acceptable Birth Control Method.

5.1.2 Olaparib and CYP3A

Patients should avoid concomitant use of drugs, herbal supplements and/or ingestion of foods known to modulate CYP3A enzyme activity (see Section 5.6.1) from the time they enter the screening period until 30 days after the last dose of study medication.

5.2 Patient enrolment and randomisation and initiation of study treatment

The Principal Investigator will:

1. Obtain signed informed consent from the potential patient before any study specific procedures are performed.
2. Patients will be assigned a unique patient identifier which should be used to identify the patient on the eCRFs and any other trial-related communications (Ecode).
3. Determine patient eligibility. See Sections 4.1 and 4.2.

4. Randomise the patient using the randomisation system which is available for this trial, answering all questions which are asked by the system including questions relative to the stratification factors.
5. The randomisation system will randomly assign treatment (olaparib or chemotherapy) and this information will be made available to the site personnel.

As patients are screened for the study, they must be allocated an enrolment code (E-code). The E-code is a 7-digit number made up of the centre number and the patient number within that particular centre (e.g., the first patient screened at centre number 0001 would be assigned the E-code E0001001, the second patient screened would be E0001002 and so on). This number is the patient unique identifier and is used to identify the patient on the eCRFs.

If a patient withdraws from participation in the study, then her enrolment/randomisation code cannot be reused.

5.2.1 Procedures for randomisation

Patient eligibility will be established before treatment randomisation. Once the eligibility of a patient has been confirmed, the Investigator (or nominated assistant) should contact the IVRS/IWRS Centralised Randomisation Centre for allocation of randomised therapy. The investigator must declare prior to randomisation their choice of chemotherapy i.e. capecitabine or vinorelbine or eribulin.

The actual treatment given to individual patients will be determined by a randomisation scheme that has been loaded into the (IVRS/IWRS) database. The randomisation scheme will be produced by a computer software program called GRand (AZ Global Randomisation system) that incorporates a standard procedure for generating random numbers.

A blocked randomisation will be generated and all centres will use the same list in order to minimise any imbalance in the number of patients assigned to each treatment group.

The randomisation scheme will be stratified based on:

- Received prior chemotherapy regimens for metastatic breast cancer (yes/no)
- ER and/or PgR positive vs ER and PgR negative
- Prior platinum for breast cancer (yes/no)

For the purpose of stratification, a patient is considered to have received a chemotherapy regimen if he or she received at least 1 cycle of chemotherapy (at least 3 infusions if weekly regimen), or if he or she progressed clinically before completing a full cycle.

Patients will be identified to the Centralised Randomisation Centre using patient E-code and date of birth.

Randomisation codes will be assigned strictly sequentially as patients become eligible for randomisation.

Eligible patients will be randomised in a 2:1 ratio as specified below:

- olaparib tablets po 300 mg twice daily
- physician's choice of chemotherapy
 - Capecitabine 2500 mg/m² po daily (divided in 2 doses) x 14 days, repeat every 21 days
 - Vinorelbine 30 mg/m² IV Day 1 and Day 8, repeat every 21 days
 - Eribulin mesylate 1.4 mg/m² or Eribulin (active substance) 1.23mg/m² IV Day 1 and Day 8, repeat every 21 days

It is recommended that patients commence study treatment as soon as possible after randomisation, and ideally within 3 days.

5.3 Procedures for handling patients incorrectly enrolled or randomised or initiated on study treatment

Patients who fail to meet the inclusion/exclusion criteria should not, under any circumstances, be enrolled or receive study treatment. There can be no exceptions to this rule.

Where patients that do not meet the selection criteria are randomised in error or incorrectly started on treatment, or where patients subsequently fail to meet the study criteria post initiation, a discussion should occur between the AstraZeneca Study Team Physician and the Investigator regarding whether to continue or discontinue the patient from treatment. Once a decision is made, Investigators need to ensure they comply with all applicable requirements for human patient protection and ethical review.

The AstraZeneca Study Team Physician is to ensure all such decisions are appropriately documented. In situations where an agreement cannot be reached, the patient should have their study therapy stopped and be withdrawn from the study.

5.4 Blinding and procedures for unblinding the study – Not Applicable

5.5 Treatments

5.5.1 Identity of study treatment(s)

AstraZeneca's Pharmaceutical Development, R&D Supply Chain will supply olaparib to the Investigator as green film-coated tablets as shown in [Table 2](#) below.

Table 2 Identity of investigational product

Investigational product	Dosage form and strength
Olaparib*	Tablet –100mg
Olaparib*	Tablet – 150mg

* Descriptive information for olaparib can be found in the Investigator's Brochure

Capecitabine, vinorelbine and eribulin will be sourced locally. Only under exceptional circumstances when this isn't feasible these chemotherapies will be supplied through AstraZeneca. Descriptive information for capecitabine, vinorelbine and eribulin can be found in the local package inserts supplied with the drug.

5.5.2 Doses and treatment regimens

5.5.3 Olaparib

Study treatment is available as a green film-coated tablet containing 150 mg or 100 mg of olaparib.

For all centres, olaparib will be packed in high-density polyethylene (HDPE) bottles with child-resistant closures. The randomised study treatment will be dispensed to patients. Each dosing container will contain sufficient medication for at least each treatment period plus overage. The planned dose of 300 mg bid will be made up of two (2) x 150 mg tablets bid with 100 mg tablets used to manage dose reductions. Tablets should be taken at the same times each morning and evening of each day, approximately 12 hours apart with approximately 240 mL of water. The olaparib tablets should be swallowed whole and not chewed, crushed, dissolved or divided. Olaparib tablets can be taken with a light meal/snack (e.g., two pieces of toast or a couple of biscuits).

No switch to olaparib will be provided in this study (i.e. chemotherapy patients will not be offered olaparib following their chemotherapy).

If vomiting occurs shortly after the olaparib tablets are swallowed, the dose should only be replaced if all of the intact tablets can be seen and counted. Should any patient enrolled on the study miss a scheduled dose for whatever reason (e.g. as a result of forgetting to take the tablets or vomiting), the patient will be allowed to take the scheduled dose up to a maximum of 2 hours after that scheduled dose time. If greater than 2 hours after the scheduled dose time, the missed dose is not to be taken and the patient should take their allotted dose at the next scheduled time.

Once patients have been discontinued from study treatment, other treatment options will be at the discretion of the investigator.

5.5.3.1 Chemotherapy

Dosing and treatment regimen information for capecitabine, vinorelbine and eribulin can be found in the local package inserts supplied with the drug. Please follow the prescribing information for toxicity management and dose reduction.

Standard or reduced dose of capecitabine can be used after the first cycle as per standard clinical practice.

5.5.4 Additional study drug- Not applicable

5.5.5 Labelling

Labels for olaparib will be prepared in accordance with Good Manufacturing Practice (GMP) and local regulatory guidelines. The labels will fulfil GMP Annex 13 requirements for labelling. Label text will be translated into local language.

Specific dosing instructions will not be included on the label; the site must complete the “Patient Dispensing Card” with the details of the dosing instructions at the time of dispensing.

The patient emergency contact details will not be on the label, unless it is a country-specific regulatory requirement, but can be found in the informed consent and the ‘Patient Dispensing Card’. For emergency purposes the patient must be in possession of the emergency contact details at all times.

5.5.6 Storage

All study drugs should be kept in a secure place under appropriate storage conditions. The investigational product label on the olaparib bottle specifies the appropriate storage. Storage conditions for chemotherapy can be found in the local package inserts supplied with the drug.

5.5.7 Management of toxicity of olaparib

Any toxicity observed during the course of the study could be managed by interruption of the dose of study treatment or dose reductions. Repeat dose interruptions are allowed as required, for a maximum of 4 weeks on each occasion. If the interruption is any longer, the study team must be informed. Study treatment can be dose reduced to 250 mg twice daily as a first step and to 200 mg twice daily as a second step. If the reduced dose of 200 mg twice daily is not tolerable, no further dose reduction is allowed and study treatment should be discontinued.

Once dose is reduced, escalation is not permitted.

5.5.7.1 Management of haematological toxicity

Management of anaemia

Table 3 Management of anaemia

Haemoglobin	Action to be taken
Hb < 10 but ≥ 8 g/dl (CTCAE Grade 2)	
Give appropriate supportive treatment and investigate causality.
 
Investigator judgement to continue olaparib with supportive treatment (eg transfusion) or interrupt dose for a maximum of 4 weeks.
 
If repeat Hb < 10 but ≥ 8 g/dl, dose interrupt (for max of 4 weeks) until Hb ≥ 10 g/dl and upon recovery dose reduction to 250 mg twice daily as a first step and to 200 mg twice daily as a second step may be considered.

Hb < 8 g/dl (CTCAE Grade 3/4)	
Give appropriate supportive treatment (e.g. transfusion) and investigate causality.
 
Interrupt olaparib for a maximum of 4 weeks until improved to Hb ≥ 10 g/dl.
 
Upon recovery dose reduce to 250 mg twice daily as a first step and to 200 mg twice daily as a second step in the case of repeat Hb decrease.

Common treatable causes of anaemia (e.g., iron, vitamin B12 or folate deficiencies and hypothyroidism) should be investigated and appropriately managed. In some cases management of anaemia may require blood transfusions. For cases where patients develop prolonged haematological toxicity (≥2 week interruption/delay in study treatment due to CTC grade 3 or worse anaemia and/or development of blood transfusion dependence), refer to dedicated section “Management of prolonged haematological toxicities while on study treatment” for the management of these cases.

Management of neutropenia, leukopenia and thrombocytopenia

Table 4 Management of neutropenia, leukopenia and thrombocytopenia

Toxicity	Study treatment dose adjustment
CTCAE gr 1-2	Investigator judgement to continue treatment or if dose interruption, this should be for a maximum of 4 weeks; appropriate supportive treatment and causality investigation
CTCAE gr 3-4	Dose interruption until recovered to CTCAE gr 1 for a maximum of 4 weeks, and dose reduction to 250 mg twice daily as a first step and 200 mg twice daily as a second step

Adverse event of neutropenia and leukopenia should be managed as deemed appropriate by the investigator with close follow up and interruption of study drug if required.

Primary prophylaxis with Granulocyte colony-stimulating factor (G-CSF) is not recommended, however, if a patient develops febrile neutropenia, study treatment should be stopped and appropriate management including G-CSF should be given according to local hospital guidelines. Please note that G-CSF should not be used within at least 24 h (7 days for pegylated G-CSF) of the last dose of study treatment unless absolutely necessary.

Platelet transfusions, if indicated, should be done according to local hospital guidelines.

Study treatment can be interrupted for CTCAE grade 1 /2 neutropenia or thrombocytopenia as per investigator's judgement. In case of CTCAE grade 3/4 neutropenia, leukopenia or thrombocytopenia, study treatment should be interrupted for a maximum of 4 weeks. Study treatment can be restarted at the same dose if an adverse event of neutropenia, leukopenia or thrombocytopenia have been recovered up to CTCAE grade 1 or less. Any subsequent interruptions will require study treatment dose reductions to 250 mg twice daily as a first step and to 200 mg twice daily as a second step.

Management of prolonged haematological toxicities while on study treatment.

If a patient develops prolonged haematological toxicity such as:

- ≥ 2 week interruption/delay in study treatment due to CTC grade 3 or worse anaemia and/or development of blood transfusion dependence
- ≥ 2 week interruption/delay in study treatment due to CTC grade 3 or worse neutropenia ($ANC < 1 \times 10^9/L$)
- ≥ 2 week interruption/delay in study treatment due to CTC grade 3 or worse thrombocytopenia (Platelets $< 50 \times 10^9/L$)

Weekly differential blood counts including reticulocytes and peripheral blood smear should be performed. If any blood parameters remain clinically abnormal after 4 weeks of dose interruption, the patient should be referred to haematologist for further investigations. Bone marrow analysis and/or blood cytogenetic analysis should be considered at this stage according to standard haematological practice.

Development of a confirmed myelodysplastic syndrome or other clonal blood disorder should be reported as an SAE and full reports must be provided by the investigator to AstraZeneca Patient Safety.

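### After a first grade 3-4 neutropenia, leukopenia or thrombocytopenia, Table 4 directs an olaparib dose reduction while the text below it permits restart at the same dose, and nothing says which governs

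*Protocol*

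**What the plan says.** Section 5.5.3 sets the starting point: "The planned dose of 300 mg bid will be made up of two (2) x 150 mg tablets bid". Section 5.5.7 names two reduction steps, 250 mg and then 200 mg twice daily, without saying which event triggers the first. It adds "Once dose is reduced, escalation is not permitted" and, for the bottom step, "If the reduced dose of 200 mg twice daily is not tolerable, no further dose reduction is allowed and study treatment should be discontinued".

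Section 5.5.7.1 then deals with neutropenia, leukopenia and thrombocytopenia in two places.

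- **Table 4, grade 3-4 row:** interrupt until recovery to grade 1, "for a maximum of 4 weeks, and dose reduction to 250 mg twice daily as a first step", with 200 mg twice daily as the second step.
- **Text after the table:** "In case of CTCAE grade 3/4 neutropenia, leukopenia or thrombocytopenia, study treatment should be interrupted for a maximum of 4 weeks". Then: "Study treatment can be restarted at the same dose if an adverse event of neutropenia, leukopenia or thrombocytopenia have been recovered" to grade 1 or less. Then: "Any subsequent interruptions will require study treatment dose reductions to 250 mg twice daily as a first step", again with 200 mg twice daily as the second step.

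Between the two stands a general sentence: "Adverse event of neutropenia and leukopenia should be managed as deemed appropriate by the investigator", with close follow-up and interruption if required.

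**The concern.** The table ties the first reduction to the grade 3-4 event itself. The text ties it to the next interruption. A site that restarts a recovered patient at 300 mg twice daily after a first event acts within the text and outside the table. A monitor checking adherence under Section 9.3 cannot tell from the protocol whether that restart is a deviation.

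Section 1.1.5 names bone marrow as the primary target organ of toxicity, and Section 1.4 presents the guideline for managing bone marrow toxicity as part of the safety management plan. The inconsistency therefore sits inside one of the trial's named risk controls. Because a reduction cannot be reversed, the passage followed at the first event affects the patient's dose for the rest of treatment.

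**Working it through.** There is no sample size, power or alpha figure to reproduce. The check sets the two passages side by side and works out the daily dose that each implies.

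**Side by side (grade 3-4, same three toxicities)**

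| Element | Table 4 | Text below Table 4 |
|---|---|---|
| Interruption | Yes, at most 4 weeks | Yes, at most 4 weeks |
| Recovery before restart | Grade 1 | Grade 1 or less |
| Dose at restart after a first event | Reduced, first step 250 mg twice daily | Same dose permitted |
| When reduction becomes required | At the event, no first-event exception | At subsequent interruptions |

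The passages agree on interruption and, in substance, on recovery. They part only on the restart dose.

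**Dose paths.** Inputs: start at 300 mg twice daily (Section 5.5.3); steps of 250 and 200 mg twice daily and no escalation (Section 5.5.7). Assumptions: each event recovers within the 4 weeks, no reduction has been made for another reason, and the site following the text uses its permission at the first event. Daily dose = 2 × single dose.

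- After event 1: table 2 × 250 = 500 mg/day; text 2 × 300 = 600 mg/day. Difference 100 mg/day; 100/600 = 16.7%.
- After event 2: table 2 × 200 = 400 mg/day; text 2 × 250 = 500 mg/day. Difference again 100 mg/day; 100/500 = 20%.
- At event 3: the table has no step left, and Section 5.5.7 calls for discontinuation if 200 mg twice daily is not tolerable; the text still provides 200 mg twice daily.

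The gap after event 2 is the same single step carried forward, not a second divergence. The percentage rises only because the denominator falls from 600 to 500.

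**Grade 1-2.** Table 4 leaves these grades to the investigator and attaches no reduction. The text also allows interruption for grade 1-2 neutropenia or thrombocytopenia, but its later clause on subsequent interruptions carries no grade limit. Read literally, that clause could require a reduction at a grade 1-2 interruption where the table requires none.

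Febrile neutropenia has its own instruction in the same section and is outside this point.

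**The case against.** **The text only permits.** It says treatment can restart at the same dose, not that it must. A site that reduces to 250 mg twice daily after the first event follows the table and breaches nothing in the text; at a later interruption the second step takes the patient to 200 mg twice daily, consistent with both. This stands. A reader might infer that the two rules are opposites and cannot both be followed. The wording does not support that: the conflict runs one way, in that the text allows what the table does not.

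**The table may give only the ladder, and the text the timing.** The first-step and second-step wording does echo Section 5.5.7. But Table 3, on anaemia, states a repeat condition where one is meant; Table 4 has none and joins the reduction directly to the interruption. This reading is possible but not written.

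**The investigator has discretion.** Section 5.5.7 says toxicity could be managed by interruption or reduction, and the sentence under Table 4 defers to the investigator. That sentence omits thrombocytopenia and is silent on restart dose, so it does not settle the matter.

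**The consequences are contained.** Both passages require interruption and recovery, and every dose involved is one the protocol allows. Blood counts are frequent, prolonged toxicity has its own work-up, an IDMC reviews safety (Section 12.4), and reductions are recorded with reasons. The primary analysis is by randomised treatment whatever was received (Section 12.1.1), so variable dosing does not invalidate the PFS comparison. All of this stands and limits the reach of the point; none of it tells a site which dose to restart.

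**Conclusion.** The point holds as an internal inconsistency in the bone-marrow toxicity rule. For a recovered first grade 3-4 event, Table 4 leads to 500 mg/day and the text permits 600 mg/day, with no order of precedence. The offset is one step (50 mg twice daily, 100 mg/day) and persists because escalation is barred. These figures rest on the assumptions listed with the dose paths.

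Two stronger inferences are not supported. A reader might conclude that sites are in fact dosing differently; the protocol shows only that they can. A reader might also conclude that the efficacy or tolerability estimates are distorted; the protocol gives no expected rate of these grade 3-4 events, so neither the number of patients affected nor any such effect can be sized. The case for correction rests on a safety instruction that cannot be applied or monitored uniformly as written.

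**What to change.** The sponsor must reconcile Table 4 and the text of Section 5.5.7.1 into one rule, worded identically in both places. It should state:

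- what applies to the restart dose after a first grade 3-4 event, and what applies after later ones;
- whether the clause on subsequent interruptions covers grade 1-2 interruptions or only grade 3-4.

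Which rule to adopt is for the sponsor's medical lead; no view is offered here. Sites should be notified so that investigators and monitors work from the same instruction. The cost is amendment wording and a clarification letter to sites.
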